Infant screening using the proposed instrument will be cost-effective using conventional criteria, and with a QTc cutoff of 460 ms in two serial follow-on ECGs triggered by an abnormal value on the QTc meter, the number of false positives is estimated to be low (~1 in 1,000) (2). We envision the parents of newborn children being informed about LQTS, a treatable disease that can cause life-threatening arrhythmias in infants, children, and young adults occurring in 1 in 2,000 births, and informed that early diagnosis is achievable by adequate screening and any required follow-on diagnostics.

The objective of the proposed project is to further develop and evaluate a diagnostic algorithm suitable for use in an inexpensive diagnostic instrument suitable for screening for LQTS in the primary care environment. We plan to develop novel technology enabling the screening of newborns for the presence of abnormal QT/QTc interval prolongation. During this phase II study we propose to test a newly built prototype (upgraded from the

prototype used in phase I), validate the new algorithm in a cohort of 1,000 newborns/children and demonstrating the ability of the QTc meter to screen newborns for LQTS and help clinicians to improve patient management and save lives. The phase II project will finalize the algorithm design from phase I and fully validate its performance in a study informed by the phase I pilot evaluation.

Aim 1: Assemble a prototype system to enable the recording of the surface ECGs with the technical specification fitting the standard technical requirements for FDA-approved clinical ECG devices. Use the upgraded prototype developed base off results from the Phase I study to record ECGs in a cohort of 1,000 newborns/children to form a learning dataset for the Aim 2. This includes 500 control subjects and 500 with LQTS.

Aim 2: Evaluation of the usability and performances of the QTc Meter in a validation study conducted at the Mayo Clinic's LQTS Clinic

Objective:

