An updated prototype QT meter has been developed following the results obtained in phase I of the study. This new device, with its new enhancements, will be able to be paired with an associated app via Bluetooth and connected with a database in the cloud. Because this device is now Bluetooth enabled it will no longer need to be directly connected to the ECG machine. Phase II of the study will involve acquiring ECG data in a cohort of up to 1,000 newborns and infants (500 controls (non-LQTS) and 500 LQTS newborns and infants) that are being seen in the Gonda SL ECG Lab (or Baldwin Building) and enrolled during their appointment for a clinically indicated 12-lead ECG. A second arm of Phase II of this study will include approaching 50 healthy subjects at the Baldwin Building to seek interest in participation which will consist of (1) 30 second device recording to help further calibrate and test the device for optimal enhancement. These 50 subjects will not be required to have a clinical or research 12-lead ECG as we will be simply testing the efficiency and accuracy of the device. LQTS will be studied in order to assess the ability of the LQTS screener to accurately detect a patient with established QT prolongation in the context of distinct and varied T wave morphologies. The advanced prototype will be placed in the same manner as the device used in Phase I of the study by being lightly placed on the child as pictured below. Similarly, we will use ultrasound gel to obtain a better reading, if applicable. Once completed, a photograph of the torso of the child will be taken from the same views as before (one aerial view and one side view) with neither the head nor the face in the picture. Coded ECG-tracings will be transmitted to the app and shared with Blue Ox Health Corporation and Minnesota Health Solutions as done previously in phase I. Additionally, coded tracings and data from the 12-lead ECG will be shared with Blue Ox Health Corporation and Minnesota Health Solutions to aid in comparison to device tracings and optimization of the algorithm. The 12-lead ECG will be obtained from the subject's medical record and coded before being shared with collaborators. Study coordinators will also review the patient's medical record to determine whether they have been diagnosed with a genetic disease.

Phase I Prototype

Phase II Prototype

Potential risks to the patient:

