Review the list of subject identifiers below and, if applicable, check the box next to each HIPAA identifier being recorded at the time of data collection or abstraction. Identifiers apply to any subject enrolled in the study including Mayo Clinic staff, patients and their relatives and household members.

Internal refers to the subject's identifier that will be recorded at Mayo Clinic by the study staff.

External refers to the subject's identifier that will be shared outside of Mayo Clinic.

Check all that apply:	INTERNAL	EXTERNAL
Name	X	
Mayo Clinic medical record or patient registration number, lab accession, specimen or radiologic image number	X	
Subject ID, subject code or any other person-specific unique identifying number, characteristic or code that can link the subject to their medical data	X	X
Dates: All elements of dates [month, day, and year] directly related to an individual, their birth date, date of death, date of diagnosis, etc. Note: Recording a year only is not a unique identifier.	X	X
Social Security number		
Medical device identifiers and serial numbers		
Biometric identifiers, including finger and voice prints, full face photographic images and any comparable images	X	X
Web Universal Resource Locators (URLs), Internet Protocol (IP) address numbers, email address		
Street address, city, county, precinct, zip code, and their equivalent geocodes		
Phone or fax numbers		
Account, member, certificate or professional license numbers, health beneficiary numbers		
Vehicle identifiers and serial numbers, including license plate numbers		
Check 'None' when none of the identifiers listed above will be recorded, maintained, or shared during the conduct of this study. (exempt category 4)	 None	 None

Data Analysis

Power analyses may not be appropriate if this is a feasibility or pilot study, but end-point analysis plans are always appropriate even if only exploratory. Provide all information requested below, or provide justification if not including all of the information.

No statistical information

Over the course of the study, we will send de-identified recordings to Minnesota Health Solutions (MHS). We will work to finalize the algorithm design and fully validate its performance.

Power Statement:

Data Analysis Plan:

Endpoints

Primary:

Secondary:

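### The 12-lead comparator goes to the collaborating companies for algorithm optimisation in the same 1,000 children used to validate the algorithm, with no lock, withheld subset or masking required

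*Protocol*

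**What the plan says.** **Data flow (Study Design and Methods, Methods).** The meter recordings go to two companies: "Coded ECG-tracings will be transmitted to the app and shared with Blue Ox Health Corporation and Minnesota Health Solutions". The reference recordings go to the same two: "coded tracings and data from the 12-lead ECG will be shared with Blue Ox Health Corporation and Minnesota Health Solutions to aid in comparison". The full purpose given for the second transfer is "to aid in comparison to device tracings and optimization of the algorithm". The 12-lead ECG is taken from the medical record and coded first. No date or order is given for its release.

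**Role of the children (Research Question and Aims).** Aim 1 is to "record ECGs in a cohort of 1,000 newborns/children to form a learning dataset for the Aim 2". The paragraph before it proposes to "validate the new algorithm in a cohort of 1,000 newborns/children". Aim 2 is "Evaluation of the usability and performances of the QTc Meter in a validation study conducted at the Mayo Clinic's LQTS Clinic", with no sample size, separate sample or masking rule of its own.

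**Data Analysis.** The section says "Over the course of the study, we will send de-identified recordings to Minnesota Health Solutions (MHS"), and then "We will work to finalize the algorithm design and fully validate its performance". The fields for power, analysis plan and endpoints are empty.

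**The concern.** A validation result is meant to show how a finished algorithm performs on children who had no part in shaping it. Here the comparator is supplied partly so that the algorithm can be improved against it, and the children concerned are the validation cohort. Coding the records hides identity but not the reference QTc.

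Two kinds of decision are exposed. One is the choice of algorithm version and settings: if several candidates are tried and the one closest to the 12-lead is kept, its agreement in those children is partly a product of the selection. The other is any handling of individual tracings, such as rejecting a poor 30-second recording, if it is done after the comparison is known. Both tend to push agreement and accuracy upwards.

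For a device intended for screening in primary care, the validation figures are what later users would rely on. Once the reference has been seen for a child, that child cannot again serve as an unseen test case.

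**Working it through.** No formula applies. The Protocol states no performance target, margin, alpha or power, so there is no figure to reproduce. The check is whether any section separates tuning from validation.

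1. **Who receives what.** Methods: meter tracings go to Blue Ox Health Corporation and Minnesota Health Solutions; 12-lead tracings and data go to the same two. The comparator is not kept with a separate party.
2. **Purpose.** Methods: comparison and optimisation. Tuning against the 12-lead is therefore an intended use.
3. **Which children.** Aims: one cohort of 1,000 (500 LQTS + 500 controls), described as learning data in Aim 1 and as the validation cohort in the preceding paragraph. Methods describe the same 500 + 500, as an upper limit. The accrual target is 500 + 500 + 50 = 1,050 (Subject Information). The further 50 are healthy subjects who need no 12-lead ECG and who serve to calibrate and test the device. Accrual is fully used up, so no further group is left that could be an independent validation sample.
4. **Lock.** Data Analysis puts finalising and validating in one sentence, with no step between them. No section fixes a version before comparison.
5. **Withholding or masking.** None is stated in the Aims, Methods, Resources or Data Analysis sections. Resources orders consent before the clinical 12-lead ECG and the meter recording after consent. That concerns the visit, not later processing.

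Steps 1 to 3 are positive statements of the Protocol. Steps 4 and 5 show that nothing in it limits their effect. If the plan is followed as written, the validation children can be the tuning children, with the comparator available to those doing the tuning.

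**Precision cost of the remedy.** If a share f of the 1,000 is reserved, the confidence interval of a validation estimate widens by about 1/√f compared with using all 1,000. The shares below are assumptions, because the Protocol gives none:
- f = 1/2 (500 children): √(1,000/500) = 1.41
- f = 1/4 (250 children): √(1,000/250) = 2.00

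**The case against.** **The output is automated.** The Protocol describes an automated QTc program, and under Innovation it names an already validated interpretation algorithm. No section has company staff reading individual tracings or choosing beats. This stands against any claim that results are read with the answer in hand. It does not meet the point about tuning: automation protects only once the version is frozen, and Methods and Data Analysis both say that the algorithm is still being optimised and finalised.

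**Sharing reference data is normal in development work.** This is correct, and for learning children it should continue. The difficulty is that the study also claims full validation in the same cohort.

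**A statistical analysis plan may add a lock or masking.** It may, and the lack of such detail would not by itself be a finding. But the double role of the cohort and the unrestricted sharing are fixed in this Protocol, and a later plan would have to override them.

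**Stronger readings that the text does not support.**
- A reader might infer that the meter result is never produced blind. The Protocol is silent on masking; it does not exclude it.
- A reader might infer that 12-lead data flow throughout the study. That timing is stated only for recordings sent to Minnesota Health Solutions; the 12-lead transfer is undated.
- A reader might infer that both records are sent for every enrolled child. The 50 second-arm subjects need no 12-lead ECG.
- A reader might infer that a reserved validation group is compromised. No such group is defined, and that is part of the defect.
- A reader might infer that the companies alone finalise the algorithm. Data Analysis says only that the study team will.
- A reader might infer a permanent, undetectable bias. The site keeps the subject codes and the source 12-lead ECGs, so missing tracings could be counted and the final version rerun on all of them. That would expose selective exclusion, but it would not undo tuning.

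**Conclusion.** The concern holds in this form: the collaborating companies receive the comparator for optimisation in the children used for validation, and the Protocol requires no lock, withheld subset or masking. Reported agreement or accuracy may therefore be optimistic.

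The size is not derivable. It depends on how many algorithm versions are compared, how flexible they are, and whether tracings are set aside after comparison, and the Protocol gives none of these. A numerical example of inflated sensitivity for LQTS would rest on invented counts. It would also rest on the diagnosis, which Methods does not list among the data shared. Knowing the 12-lead QTc bears directly on QTc agreement and only indirectly on LQTS status.

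The conclusion assumes that the 1,000 children in the Aims and in Methods are one cohort, which the matching 500 + 500 and the accrual total support, and that no separate plan already reserves children. The point should be settled before further 12-lead data are released, but it does not make the study unworkable.

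**What to change.** Amend Research Question and Aims and the Methods together.

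1. Designate part of the 1,000 children as validation only, by a rule set in advance, for example those enrolled after a stated date. State the number, and make sure that both LQTS and control children are included. Any child whose 12-lead data have already been released belongs to the learning part.
2. For validation children, the clinical site holds the 12-lead data and the diagnosis.
3. The collaborators name and lock an algorithm version, then return a QTc or a not-readable code for every meter tracing they were sent, in a dated file.
4. Only then is the reference released. The site matches the outputs to it and reports the not-readable rate beside the agreement or accuracy results.
5. Paired release stays as written for the learning children.

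**Cost.** There are fewer children for tuning, and the developers wait for the validation references. The validation estimate rests on fewer than 1,000 children, with the interval widening shown in the working. The change needs no additional patients, visits or procedures; it alters the order of a data transfer and adds one locked output file.

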We propose a novel inexpensive diagnostic device specifically designed to support widespread screening for LQTS in the primary care setting. The device will be physically small, easily cleanable, battery powered, and Bluetooth connected to obtain recordings on an associated device. It will connect to the patient with conductive pads that are held against the patient's chest (connections RA, LL, and RL). The objective of the proposed project is to specify, develop, and evaluate a diagnostic algorithm suitable for use in an inexpensive diagnostic instrument suitable for screening for LQTS in the primary care environment. The follow-on phase II project will finalize the algorithm design, test the newly developed prototype, and fully validate its performance in a study informed by the phase I pilot evaluation.

The envisioned end product will be based off of the results obtained from phase II of the study. At an infant well-child checkup in the primary care environment, a technician/study coordinator will press the device to the infant's chest for 30 seconds. The device will be paired with Bluetooth that can be connected to either an app or laptop that displays the results from that recording and stored via the cloud. It will be designed to be very easy to use. The proposed project concentrates on algorithm design. The phase I prototype will be assembled using an FDA approved ECG that the PI designed for QRS Diagnostic, LLC that will be modified to collect data in support the proposed development activities. A follow-up phase of the project will be used to test a more advanced prototype from the results obtained in phase I. Enrollment may also be discussed and arranged prior to the patient's visit via telephone.

[figure not shown]
Background (*Include relevant experience, gaps in current knowledge, preliminary data, etc.:*)

Infants, children, adolescents, and young adults are vulnerable to undiagnosed and potentially lethal cardiovascular diseases. The younger age range includes the clinically important group of infants at risk for sudden infant death syndrome (SIDS). Long QT syndrome (LQTS) is a genetic disorder characterized by QT prolongation, and is associated with potentially life-threatening cardiac arrhythmias that may lead to syncope, seizures, cardiac arrest, or sudden death. Although LQTS is potentially lethal, very effective therapies are available once LQTS is diagnosed. The development of an accurate and inexpensive instrument that screens for

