Infants and children are vulnerable to undiagnosed and potentially lethal cardiovascular diseases including the clinically important group of infants at risk for Sudden Infant Death Syndrome (SIDS). LQTS is a genetic disorder characterized by QT prolongation, T wave abnormalities on the ECG, potentially life-threatening cardiac arrhythmias (leading to syncope, cardiac arrest or sudden death) often triggered by emotional or physical stress, and the availability of very effective therapies (1). The onset of life-threatening arrhythmias is gene-specific and occurs mostly below age 15 (2). Mortality has been reduced from over 50% (for the highest risk subset) to approximately 1% over ~15 years follow-up for properly managed patients (1). On the basis of the identification of disease-causing mutations in infants with a QTc > 460 ms from a cohort of more than 44,000 infants with an ECG in the 3rd-4th week of life, the prevalence of LQTS has been estimated at about 1/2,000 live births in a population primarily of European descent (3). This allows a relatively simple calculation of how many new neonatal cases of LQTS can be expected each year in any country with a similar genetic background. It has been established, again by the presence of disease-causing mutations, that approximately 10% of SIDS may stem from LQTS-triggered sudden cardiac deaths (SCD)(4,5) and that LQTS contributes also to stillbirths (6,7). The combined observations that cardiac arrest or SCD is the sentinel event in 12-13% of affected patients outside the neonatal period (8), and that mortality is reduced dramatically among patients appropriately treated, suggest that early therapy has the potential to prevent SCD in the affected children (9). Thus, expectant management of a patient with a known diagnosis of LQTS without therapy is no longer acceptable (1). Recognizing this, treatment with β -blockers is now considered to be a Class I or IIa guidelines recommendation for almost all patients with a clinical diagnosis of LQTS (10). It goes without saying that affected individuals not yet diagnosed escape the possibility of being treated. Hence, an important clinical objective should be to identify the largest possible number of affected individuals at the earliest possible time.

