Potential risks of the protocol include skin reactions to the ECG electrodes or ultrasound gel. This device currently does not have an indicated use for patients with cardiac devices therefore to avoid this unknown risk we will not be enrolling any patients with a pacemaker/ICD.

Resources: *Describe the available resources to conduct the research (personnel, time, facilities, mentor commitment, etc.):*

Screening will utilize the study coordinator and nurse of Mayo Clinic's LQTS Clinic who will review the schedule of returning, established LQTS children who would meet the study's eligibility criteria. If eligible, the infant/child's parents would be contacted at their annual clinical evaluation and informed of the study. If the parent agrees, consent will be obtained prior to the child's clinical 12-lead ECG in the Gonda SL ECG Lab. The study procedure, i.e. the application of the QTc Meter, will be initiated following consent.

(1a) This is a multisite study involving Mayo Clinic and non Mayo Clinic sites. *When checked, describe in detail the research procedures or activities that will be conducted by Mayo Clinic study staff.*

(1b) Mayo Clinic study staff will be engaged in research activity at a non Mayo Clinic site. *When checked, provide a detailed description of the activity that will be conducted by Mayo Clinic study staff.*

Subject Information

Target accrual is the proposed total number of subjects to be included in this study at Mayo Clinic. A "Subject" may include medical records, images, or specimens generated at Mayo Clinic and/or received from external sources.

Target accrual: 1,050 subjects

Subject population (children, adults, groups):

Newborns/Children ages 5 and under

Inclusion Criteria:

1. Infants/Children (Day 0-Age 5)
2. Long QT Syndrome (LQTS)
3. Newborns without LQTS (Controls)
4. Parental willingness to provide informed consent and follow the study protocol

Exclusion Criteria:

5. Children > 5 years old
6. Those with genetically elusive LQTS
7. Infants with congenital heart disease
8. Infants born <32 weeks EGA
9. Patients with a cardiac device implant (pacemaker/ICD)

Research Activity

Check all that apply and complete the appropriate sections as instructed.

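### LQTS cases come from established patients who are probably mostly treated; treatment status is not recorded, so detection may not carry over to untreated infants

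*Protocol*

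**What the plan says.** **Source of cases.** Under Resources, the LQTS Clinic's coordinator and nurse "review the schedule of returning, established LQTS children who would meet the study's eligibility criteria". If a child is eligible, "the infant/child's parents would be contacted at their annual clinical evaluation and informed of the study". Study Design and Methods adds that subjects are enrolled at an appointment for a clinically indicated 12-lead ECG, but gives no separate route for newly found, untreated cases.

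**Treatment of diagnosed patients.** The Background states that "expectant management of a patient with a known diagnosis of LQTS without therapy is no longer acceptable" and that beta-blocker treatment "is now considered to be a Class I or IIa guidelines recommendation for almost all patients with a clinical diagnosis of LQTS". It also observes that "affected individuals not yet diagnosed escape the possibility of being treated".

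**Intended use.** The Objective section describes the end product: "At an infant well-child checkup in the primary care environment, a technician/study coordinator will press the device to the infant's chest for 30 seconds". Research Question and Aims says Phase II is to demonstrate that the meter can screen newborns for LQTS, and that the recordings of 500 LQTS and 500 control children form a learning set. The Innovation section says the algorithm will sort children into low or high likelihood of LQTS on the basis of the QTc.

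**Data taken from the chart.** Apart from obtaining the 12-lead ECG, Study Design and Methods describes one item: "Study coordinators will also review the patient's medical record to determine whether they have been diagnosed with a genetic disease". The inclusion and exclusion lists under Subject Information do not mention medication.

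**The concern.** A screening test is judged by how well it finds cases among the people who will be screened. Here the cases are children already diagnosed and under follow-up, while the target is infants nobody has yet diagnosed. On the protocol's own reasoning these groups differ systematically in treatment: therapy is recommended for nearly all of the first and cannot reach the second.

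If treatment alters the features that the meter reads, the proportion of cases detected describes managed children. A threshold or algorithm tuned on these recordings may likewise fit them better, or worse, than untreated infants. Treatment may also follow case status in the learning set, which would mix it with the label the algorithm is meant to learn. Without a treatment field in the analysis data, none of this can be examined there.

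What is at stake is the claim that the meter can screen newborns for LQTS. Device-to-ECG agreement in the same child is a separate matter.

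**Working it through.** **1. The protocol's own figure.** The planned groups are 500 LQTS, 500 controls and 50 healthy subjects for device testing: 500 + 500 + 50 = 1,050. This matches the target accrual. No sample size or power figure is in dispute; the Data Analysis section gives none.

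**2. Studied cases against target infants.**

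| | LQTS group as recruited | Infants to be screened |
|---|---|---|
| Diagnosis | Established, returning (Resources) | Not yet diagnosed (Objective, Background) |
| Therapy | Recommended for almost all (Background) | None, because undiagnosed (Background) |
| Setting | Annual LQTS Clinic evaluation | Primary care well-child visit |
| Treatment status recorded | Not described | Not applicable |

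Two further points make treatment more likely among the cases. Genetically elusive LQTS is excluded, so enrolled cases should have an identified genetic cause; and the screening scheme cited in the Background recommends beta-blockers once a mutation is found. Both support an inference. Neither is a count of treated children.

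**3. How far a pooled figure can miss the target.** Let p be the treated share of cases, and S_T and S_U the sensitivity in treated and untreated cases.

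Pooled sensitivity = p × S_T + (1 − p) × S_U

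Pooled sensitivity − S_U = p × (S_T − S_U)

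The protocol gives none of these inputs. If S_T and S_U differed by 10 percentage points in either direction (an assumption), the pooled figure would miss S_U by:

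- p = 0.80: 0.80 × 10 = 8 points
- p = 0.90: 0.90 × 10 = 9 points
- p = 0.95: 0.95 × 10 = 9.5 points

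If treatment makes no difference to detection, the error is zero. The direction is not known.

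**4. What 500 cases say directly about untreated children.** Number untreated = 500 × (1 − p). Exact (Clopper-Pearson) 95% intervals, with an observed sensitivity of 80% assumed throughout:

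| Assumed treated share | Untreated cases | Detected | 95% interval |
|---|---|---|---|
| All 500 pooled | – | 400 of 500 | 76.2% to 83.4% |
| 80% | 100 | 80 | 70.8% to 87.3% |
| 90% | 50 | 40 | 66.3% to 90.0% |
| 95% | 25 | 20 | 59.3% to 93.2% |
| 98% | 10 | 8 | 44.4% to 97.5% |

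The pooled interval is about 7 points wide (83.4 − 76.2 = 7.2). With 50 untreated cases it is about 24 points wide (90.0 − 66.3 = 23.7), and with 10 about 53 (97.5 − 44.4 = 53.1). A precise pooled result could thus sit on little direct evidence about untreated infants.

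**The case against.** **The treated share is not stated.** A reader might infer that the protocol itself says almost all of these children are on beta-blockers. It does not. The Background reports a guideline recommendation, untreated children are not excluded, and nothing is said about the controls' medication. That many cases are recorded on treatment is a reasonable inference and no more.

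**No shift in milliseconds can be derived.** It is tempting to assume slower heart rates on treatment, apply Bazett's formula and show a child crossing 460 ms. The documents do not support this. They give no drug effect on heart rate or QTc. Bazett is named for the cited neonatal scheme, and no correction formula is fixed for the meter. The 450, 460 and 470 ms points belong to that scheme or to follow-on ECGs after an abnormal meter value. If QT follows the cube root of RR, Bazett's QTc changes with rate, but a cube-root correction gives no change at all. The size would come from the chosen formula and rates.

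**The study has a narrower purpose too.** Study Design and Methods says LQTS children are included to test detection of established QT prolongation across T wave shapes, with the same child's 12-lead ECG for comparison. Treatment is then common to both recordings and need not bias agreement. This stands, but the Aims and Innovation sections go further, to newborn screening and risk classification, and there the mismatch applies.

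**The information is not lost.** One might conclude that treatment effects can never be separated afterwards. In fact the medical record number and a subject code are kept internally, and the identifiers section says such identifiers allow new data points to be added. The chart review sentence is also not presented as a complete field list. So the status can be retrieved, but only if someone plans to retrieve it.

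**An SAP might stratify.** An SAP that is not shown could do so, but only if treatment status is collected. Recruitment and data collection are set in the protocol.

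**Conclusion.** The concern holds as a mismatch between the cases studied and the infants to be screened. As described, the study would measure case detection in established, probably mostly treated patients, with no described step to record treatment, while aiming to demonstrate newborn screening. Detection figures, and any threshold or algorithm tuned on these recordings, may not transfer to untreated infants. Same-child agreement with the 12-lead ECG is not called into question.

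The size is unknown because the treated share and any treatment effect are not in the documents. On assumed treated shares of 80% to 98%, between 100 and 10 of the 500 cases would inform directly on untreated children. The conclusion rests on two premises: that the Resources route supplies most LQTS cases, and that clinic practice broadly follows the recommendation the protocol cites. Confidence is moderate, and the point is a should-fix.

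**What to change.** 1. Extend the existing chart review to record beta-blockers and any other rate- or QT-affecting drug in use at the time of each recording, for cases and controls, and carry this as a coded field with the tracings used for algorithm work.
2. Report case detection separately for treated and untreated LQTS recordings, with exact intervals.
3. Base the screening claim on untreated recordings. If these are too few, limit the conclusion to agreement with the 12-lead QTc in established patients.

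The cost is one or two fields from charts that are already opened, and one stratified table. The downside is that the untreated group will probably be small and its estimate imprecise, so the study may have to make a more modest claim. No change to any child's treatment is implied.

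### The control criterion says newborns only while cases may be up to age 5, and other sections word the age range differently, so same-age controls are not ensured

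*Protocol*

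**What the plan says.** The protocol states the age range of the study groups in several places.

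- **Subject Information, Inclusion Criteria.** Criterion 1 admits "Infants/Children (Day 0-Age 5". Criterion 2 names LQTS without an age. Criterion 3 reads "Newborns without LQTS (Controls". The exclusion of children older than 5 years is not specific to either group.
- **Subject Information, subject population.** "Newborns/Children ages 5 and under", with no distinction between groups.
- **Research Question and Aims, Aim 1.** The prototype is used "to record ECGs in a cohort of 1,000 newborns/children to form a learning dataset for the Aim 2", and this cohort is split into 500 controls and 500 with LQTS.
- **Study Design and Methods.** The cohort is "500 controls (non-LQTS) and 500 LQTS newborns and infants", "enrolled during their appointment for a clinically indicated 12-lead ECG".
- **Resources.** Staff will "review the schedule of returning, established LQTS children", whose parents "would be contacted at their annual clinical evaluation".

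Newborn is not defined, and nothing in the protocol ties the controls' ages to the cases' ages.

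**The concern.** Within one eligibility list the control group is given a narrower age word than the case group. A coordinator reading it cannot tell whether a three-year-old without LQTS may be enrolled as a control: criterion 1 says yes and criterion 3 says no.

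The Resources text makes this matter in practice. Children who return each year with an established diagnosis are mostly past the newborn period. Newborn controls set against such cases would give a specificity and a sensitivity that describe children of different ages. The same 1,000 recordings are meant both to develop the algorithm and to show that the meter detects LQTS, so any age difference between the groups would carry into both uses. Analysis could adjust only within the ages that both groups share. It could not supply older controls whom the eligibility rule had kept out.

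**Working it through.** **1. The plan's own total.** 500 controls + 500 LQTS + 50 healthy device-test subjects = 1,050, which matches the target accrual. The numbers agree; the problem lies in who may fill the 500 control places.

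**2. Age range by group, as each place states it.**

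| Place | Cases | Controls |
|---|---|---|
| Inclusion criteria 1 to 3 | day 0 to age 5 | newborns |
| Subject population line | up to age 5 | up to age 5 |
| Aim 1 | newborns/children | newborns/children |
| Methods | newborns and infants | newborns and infants |

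Only the first row separates the groups. The other three give a common range but do not agree on it: the Methods wording stops at infants, the population line runs to age 5, and Aim 1 gives no upper age.

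**3. How cases arrive.** Resources points to annual evaluations of established patients. The Methods are wider, since the whole cohort is enrolled at appointments for a clinically indicated ECG, so annual visits are not the only route. A mainly older case group is likely but not certain.

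**4. Does age matter for QT, on the protocol's own evidence?** In the first weeks of life, yes. The Background says the QT pattern has settled by the third to fourth week. The cost-effectiveness section says that screening on day 3 gives many false positives. Both statements concern only the first weeks, and neither gives a size for any difference at later ages.

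**5. How much the choice of wording matters for overlap (illustration only).** Assume control ages spread evenly over (0, a) and case ages evenly over (0, L), with a no greater than L. The expected number of cases within the controls' age range is 500 × a/L. The 28-day meaning of newborn is an assumption.

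- a = 28 days, L = 5 years: 500 × 0.0153 = about 8
- a = 28 days, L = 1 year (cases limited as in the Methods): 500 × 0.0767 = about 38
- a = 1 year, L = 5 years: 500 × 0.20 = 100
- one range for both groups (a = L): all 500

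These counts show how far the overlap depends on the wording. They do not measure bias in the meter.

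**6. Cost of spreading the controls over age.** The exact (Clopper-Pearson) 95% limits for x correct out of n are the 2.5% quantile of Beta(x, n − x + 1) and the 97.5% quantile of Beta(x + 1, n − x). Taking an observed newborn specificity of 95% for illustration:

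- 475 of 500: 92.7% to 96.7%
- 95 of 100: 88.7% to 98.4%

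**The case against.** The strongest reply is that criterion 3 is shorthand. No child can meet both criterion 2 and criterion 3, so the list must be describing two groups under the general range of criterion 1. The population line, Aim 1, the Methods and the upper-age exclusion all treat the groups alike. On that reading overlap is permitted, and what remains is a wording fault together with the absence of any statement on age comparability. This reading is plausible. It does not remove the contradiction, because staff enrol from the eligibility list and the sections it would defer to disagree among themselves.

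Three stronger inferences are tempting, and the documents do not support them.

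- **That age alone would nearly separate the groups, so reported accuracy would be largely an age effect.** Under the even-spread assumption with newborn controls and cases up to age 5 or 6, a rule using age only has an AUC of 0.90 to 0.99. But the meter is described as classifying on QTc from the ECG, and nothing makes age an input. If both groups follow the same range, the age-only AUC is 0.50.
- **That the mutation yields in the Background show age dependence.** The figures are over 40% of infants with QTc above 470 ms, and over 90% of those still prolonged at one year. The second group is selected for persistence, which could produce the contrast without any effect of age.
- **That algorithm training is confounded.** This is possible but not shown. It would need training on case status with age-linked ECG features, which the protocol does not describe.

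Reporting accuracy by age band may properly be left to an analysis plan that is not shown, and its absence here is not a fault.

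**Conclusion.** The contradiction stands and should be fixed. Criterion 3 as written restricts controls to an undefined newborn group, cases may be up to age 5, and the other age statements do not agree with it or with each other.

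The consequence is conditional. If criterion 3 is applied literally and most cases come from annual visits, case status could be confounded with age in the learning and validation data. If the common range governs, overlap is allowed but not ensured. The protocol contains no QTc distribution by age and no age distribution for either group, so no size can be put on the bias. The comparison of the device with the 12-lead ECG is made within the same child and does not depend on the controls' ages.

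**What to change.** Reconcile the age wording in Aim 1, the Methods, the subject population line and the inclusion criteria to one range that applies to cases and controls alike. Reword criterion 3 to that range. If criterion 1 governs, it could read: infants/children (day 0 to age 5) without LQTS. If the Methods wording governs, both groups should be narrowed together; the sponsor must choose. Then state that the 500 controls are recruited across the same broad age bands as the cases, with a newborn band kept because newborn screening is the stated use.

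The change needs wording edits and some steering of control recruitment by age. Accrual stays at 1,050 and no procedure is added. The cost is fewer newborn controls, and so the wider interval for newborn specificity shown above. The change does not add newborn cases.
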